- Overall study success criteria of at least a 30% difference between the test device group and the placebo group, comparing the proportion of individual successes in each group.
- It is anticipated that about 50% of subjects in the test device group and about 20% of subjects in the placebo group will meet the individual success criteria, and
- Intended application of a two-tailed test with an alpha value of 0.05 and Power of 0.8

- the sample size of 25 available subjects per group (test group and the control group, separately) has been determined using the following reference calculator: *Hypothesis Testing: Categorical Data - Estimation of Sample Size and Power for Comparing Two Binomial Proportions* in Bernard Rosner's *Fundamentals of Biostatistics*.

For the purposes of sample size calculation, a subject loss-to-follow-up of 20% is anticipated.

Therefore, a minimum starting sample size of 30 evaluable subjects in each group is needed to ensure that a sufficient number remains at the end of the trial (25 subjects per group) for any significant differences found between groups to be considered statistically valid and representative of the general population being sampled. This results in a total of 60 subjects being enrolled in this study across both study procedure groups.

RANDOMIZATION

Subject allocation to procedure group will be via variable block randomization with varying block sizes of two and four used at random to minimize the likelihood of predicting the next procedure group assignment. In addition, randomization will be stratified by Fitzpatrick Skin Type grouping

Randomization will be attained using computer generation sequence methodology, ensuring that the randomization methodology and the generated allocation sequence is concealed from the investigator and subjects.

Concealment will be insured as follows:

- Each computer-generated randomization sequence is unique and will therefore not be able to be replicated.
- Randomization will occur to either 'Test Group A' or 'B' rather than to a tests or placebo group, and only the study Sponsor will know which assignment corresponds to the active devices and which corresponds to the fake device. The Sponsor will not reveal this information to any source (investigators, subjects, or study Monitor) until the final study data analysis is complete.

TRIPLE BLIND DESIGN

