CHANGE IN SUBJECT SELF-REPORTED VAS PAIN RATING FROM BASELINE TO STUDY ENDPOINT

Primary efficacy outcome measure for this clinical study will be a statistically significant difference in the proportion of subjects between test and control groups who achieve a clinically meaningful and statistically significant decrease in self-reported VAS pain rating from baseline to study endpoint.

Subjects meeting Individual Success Criteria

The individual subject success criteria is defined as a 30% or greater decrease in self-reported VAS pain rating at study endpoint relative to baseline.

Overall Study Success Criteria.

Overall study success criteria is defined as at least a 30% difference between procedure groups, comparing the proportion of individual successes in each group. It is anticipated that about 50% of subjects in the test group will meet the individual success criteria and about 20% of subjects in the control group will meet the individual success criteria.

Evaluation Time Points

The study end evaluation time point at which study success will be analyzed is within 24 hours following completion of the three-week procedure administration phase with the Multi Radiance Medical® MR5® Prototype Device. Study success will be evaluated at endpoint relative to baseline.

Hypotheses

- *Null Hypothesis:* There will be no statistically significant difference in the proportion of individual successes, as defined, between the test and control groups.

- *Alternative Hypothesis:* There will be a statistically significant difference in the proportion of individual successes, as defined, between the test and control groups, to the effect of 30% or greater.

PRIMARY EFFICACY OUTCOME STATISTICAL EVALUATION METHODS

Intent to Treat (ITT) Principle: Primary efficacy analysis will be according to the intent to treat (ITT) principle; wherein subjects will be included in the analysis if they were randomized to study procedure group, had a valid baseline (pre-procedure) visit including the required Lateral Epicondylitis pain VAS recordings; and received at least the first study procedure administration.

Missing data will be handled through all of the following methods:

- *Last Observation Carried Forward (LOCF):* by carrying forward the last recorded observation to fill in the subsequent missing value.

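### The plan does not say whether a significant difference below 30 percentage points counts as success, and a 30-point hurdle is met only about half the time at the plan's own assumed rates

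*Combined protocol and SAP*

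**What the plan says.** All references are to the combined protocol and SAP.

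- **Statistical Analysis, primary efficacy outcome:** "Primary efficacy outcome measure for this clinical study will be a statistically significant difference in the proportion of subjects between test and control groups". The null hypothesis is in the same terms: "There will be no statistically significant difference in the proportion of individual successes, as defined, between the test and control groups".
- **Statistical Analysis, the success definition under its own heading:** "Overall study success criteria is defined as at least a 30% difference between procedure groups, comparing the proportion of individual successes in each group". No p-value is mentioned. Rationale for Sample Size repeats it: "Overall study success criteria of at least a 30% difference between the test device group and the placebo group".
- **Statistical Analysis, alternative hypothesis:** a "statistically significant difference in the proportion of individual successes, as defined, between the test and control groups, to the effect of 30% or greater".
- **Rationale for Sample Size:** the assumed rates are "about 50% of subjects in the test device group and about 20% of subjects in the placebo group", and the operating characteristics are "Intended application of a two-tailed test with an alpha value of 0.05 and Power of 0.8". The analysable number is 25 per group and the starting number is 30 per group.
- **Primary Efficacy Outcome Statistical Evaluation Methods:** Fisher's exact test and an ANCOVA on mean VAS change are both listed as the primary analysis. The tipping-point analysis is solved for a p-value of 0.05.

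No section says which statement decides success.

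**The concern.** The practical question is whether a statistically significant difference smaller than 30 points is a success. The primary outcome says yes. The success definition and the alternative hypothesis say no. The results are meant to support a De Novo submission, so this should not be left to be settled once the data are known.

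The 30-point threshold is also the difference the plan assumes to be true. A threshold placed on the expected value of the estimate is cleared about half the time, and adding subjects does not change that. The plan gives no probability of meeting its own success definition.

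**Working it through.** **Inputs.** Device rate 0.50, placebo rate 0.20, two-sided alpha 0.05, power 0.8, and 25 to 30 analysed per arm, all from Rationale for Sample Size. Fisher's exact test is the named test. The 30% is read as percentage points, since 50% − 20% = 30 points.

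**Plan's own figure.** The usual normal-approximation formula is n = [1.96·√(2·0.35·0.65) + 0.842·√(0.25 + 0.16)]² / 0.30² = (1.322 + 0.539)² / 0.09 ≈ 38.5, so 39 per arm, or 45 with continuity correction. The stated 25 is not reproduced. Exact Fisher power is 51.0% at 25 per arm and 59.6% at 30. That shortfall is a separate sample-size error.

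**Why the hurdle gives about one half.** The observed difference has mean 0.30 and standard error √[(0.25 + 0.16)/n], which is 0.128 at n=25 and 0.117 at n=30. The distance from the mean to the hurdle is (0.30 − 0.30)/SE = 0, so the probability is near 50% for every n. It moves around 50% only because responders are whole numbers: the smallest qualifying gap is 8 responders at 25 or 26 per arm (7.5 and 7.8 rounded up) and 9 at 27 to 30 (8.1, 8.4, 8.7 and 9.0).

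**Exact values.** For each rule, sum Bin(x; n, 0.5)·Bin(y; n, 0.2) over all pairs (x, y) that satisfy it. Significance means two-sided Fisher p≤0.05 with the device ahead. The hurdle means 10(x − y) ≥ 3n.

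| n per arm | Significant | ≥30 points | Both | First two disagree |
|---|---|---|---|---|
| 25 | 51.0% | 50.5% | 50.5% | 0.5% |
| 26 | 53.7% | 54.1% | 53.4% | 1.1% |
| 27 | 55.0% | 45.7% | 45.7% | 9.3% |
| 28 | 57.5% | 49.3% | 49.3% | 8.2% |
| 29 | 57.2% | 52.8% | 52.8% | 4.5% |
| 30 | 59.6% | 56.1% | 56.1% | 3.5% |

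**Unequal arms.** With general arm sizes the hurdle is x/n1 − y/n2 ≥ 0.30. Disagreement is 10.5% at 25 device v 27 placebo and 15.2% at 30 device v 28 placebo. Unequal arms are likely. Subjects are randomized before the stabilization phase, they leave if the 3-day mean VAS is below 50 (Continued Study Eligibility Evaluation), and the ITT definition drops those without a valid baseline or a first procedure.

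**Larger samples (not planned).** At 45 per arm Fisher power is 81.5% and the hurdle is met 50.4% of the time. At 100 per arm the hurdle is met 53.4% of the time.

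**Sensitivity, both conditions, placebo 20%.** A true device rate of 45% gives 35.0% (25 per arm) and 39.0% (30 per arm); 55% gives 65.7% and 72.0%. Reaching 80% needs a true device rate of 60.6% or 58.0% respectively.

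**Results the text cannot class.** 13/30 v 5/30: 43.3% − 16.7% = 26.7 points, p=0.047; significant but under the hurdle. 16/26 v 8/26: 8/26 = 30.8 points, p=0.0505; over the hurdle but not significant.

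**Tipping point.** At 30 per arm with 5 placebo responders, p≤0.05 needs 13 device responders and 30 points needs 14. At 25 per arm both need 13.

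**The case against.** A reader might infer that the plan promises an 80% chance of a 30-point difference. It does not. The power figure is attached to the two-tailed test, and no section gives 80% as the chance of clearing the hurdle. The fair criticism is that the chance of meeting the success definition is not given at all.

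A reader might also infer that the hurdle is what pulls the trial from 80% to about 50%. At the planned sizes it does not. Fisher's test alone gives 51.0% and 59.6%; the hurdle removes a further 0.5 points at 25 per arm (51.0 − 50.5) and 3.5 at 30 (59.6 − 56.1), with a maximum of 9.3 at 27. Most of the gap is the sample-size error.

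Nor are there three rules that differ in practice. With equal arms of 25 to 30, the hurdle alone and the hurdle plus significance decide alike except at 26 per arm, in 0.8% of trials. Hypotheses are not decision rules either, and Expected Results speaks of significantly more responders in the test group, so a joint reading is available. It is not stated, however, and the primary outcome still asks for significance only.

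The tipping-point section first defines its target as the point where the study conclusion changes, which would follow any governing rule. Only its p-value sentence needs aligning. Finally, requiring a minimum observed effect is a legitimate sponsor choice; the defect is that the choice is not made clear.

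**Conclusion.** The point holds and should be fixed before unblinding. One ambiguity matters: does significance below 30 points count as success? At the assumed rates the significance rule and the 30-point rule disagree in about 0.5% to 9% of trials with equal arms of 25 to 30, and in about 10% to 15% in the two unequal cases checked. Any rule containing the hurdle is met in about half of trials whatever the sample size.

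This rests on three assumptions: true rates of 50% and 20%, 25 to 30 analysed per arm, and the 30% being in percentage points. Under a relative reading the difference criterion would be met about 95% to 96% of the time, but the pairing with 50% v 20% does not support that reading. The documents give no sign that anyone intends to pick the rule after seeing the data; the text merely leaves that possible.

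**What to change.** Before unblinding, state one governing rule in both Rationale for Sample Size and Statistical Analysis, and say that the 30% is in percentage points. Either:

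- **(a)** Success is two-sided Fisher p≤0.05 favouring the device. Report the difference with its 95% confidence interval, keep 30 points only as a planning assumption, and delete the 30% clause from the alternative hypothesis. Stated probability of success: about 51% at 25 per arm and 60% at 30.
- **(b)** Success is two-sided Fisher p≤0.05 favouring the device and an observed difference of at least 30 points, written as a joint rule. Stated probability: about 50% at 25 per arm and 56% at 30.

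Under either option, make the tipping-point target match the governing rule; under (b) that means both conditions. State that the ANCOVA is supportive and cannot by itself establish or overturn success.

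The cost is wording only, with no extra subjects. Option (a) gives up the minimum-effect hurdle. Option (b) holds the chance of success near 50% at the assumed rates whatever the sample size. Neither option cures the separate sample-size shortfall.

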Subjects will be recruited from three different sites and among the licensed health care provider's test site's pool of patients who are currently being treated for, or who are seeking treatment for Lateral Epicondylitis, or from patients who respond to the following recruitment materials, if needed.

Flyer

WANTED

ADULTS WITH LATERAL EPICONDYLITIS, ONGOING
FOR ONE MONTH, FOR A CLINICAL STUDY
OF THE EFFECTS OF LOW-LEVEL LASER LIGHT ON REDUCING LATERAL
EPICONDYLITIS.

**THIS STUDY INVOLVES SIX LASER LIGHT PROCEDURES, TWO TIMES A WEEKS FOR
THREE WEEKS WITH THE MULTI RADIANCE MEDICAL® MR5® LASER AT THE TEST
SITE.**

THERE IS THREE VISITS PRIOR TO LASER LIGHT PROCEDURES WITH ONE MORE
VISIT TO THE TEST SITE
ONE MONTH AFTER THE LAST LASER LIGHT PROCEDURE.

YOU WILL RECEIVE \$450 IF YOU FINISH THE STUDY.

FOR MORE INFORMATION PLEASE CONTACT:

<PI name>
<test site name & location>
<phone # and/or e-mail>

Newspaper Ad

**Lateral Epicondylitis
Research Study**

This study is to see if the Multi Radiance Medical® MR5® LASER, a non-invasive, investigational device that uses low-level laser light, can help to relieve symptoms of Lateral Epicondylitis pain longer than one month in duration.

The study involves ten visits to a test site and recording some information at home.

You will receive \$450 if you finish the study. Please contact
<PI name> at
<test site name & location> at
<phone and/or e-mail> for details.

Compensation

A subject will be paid a stipend of \$450.00 USD for their participation in the study upon completion. Subjects will not be charged for the cost of the study procedures administered with the Multi Radiance Medical® MR5® Prototype Device for the cost of any other directly related evaluations or measurements that occur as part of his or her participation in the study.

Sample size

There will be 60 subjects evaluated for eligibility in this clinical study:

- 30 subjects in the active procedure group
- 30 subjects in the control procedure group (Placebo)

Rationale for sample size

Based on the following parameters established for the purposes of assessing efficacy of the Multi Radiance Medical MR5 Prototype Device in this clinical study using the Fischer's Exact test to assess the primary endpoint.

- Individual subject success criteria is defined as a 30% or greater reduction in self-reported Degree of Pain rating on the 0-100 VAS from baseline to study endpoint evaluation.

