- *Tipping Point Analysis:* Tipping point analysis will be used to examine the impact of missing data on the study conclusion. Tipping point analysis is defined as the difference in means (for continuous data) or the difference in the number of events (for binary data) between treatment groups in the missing cohort at which the study conclusion is changed. A tipping point analysis replaces the missing value with other values so that the resulting p-value is equal to the pre-specified significance level (i.e. $\alpha=0.05$, 2-sided).
- *Multiple Imputation Analysis:* Multiple imputation analysis is a strategy to handle missing values in a clinical trials wherein each missing value is replaced with a set of plausible values that represent the uncertainty about the right value to impute. Multiple imputation does not attempt to estimate each missing value through simulated values, but rather to represent a random sample of the missing values. This process results in valid statistical inferences that properly reflect the uncertainty that results from missing values, such as valid confidence intervals for parameters.

Multiple imputation inference involves three distinct phases:

1. The missing data are filled in m times to generate m complete data sets.
2. The m complete data sets are analyzed by using standard statistical procedures.
3. The results from the m complete data sets are combined for the inference.

Multiple imputation usually assumes that the data are missing at random (MAR). That is, for a variable Y , the probability that an observation is missing depends only on the observed values of other variables, not on the unobserved values of Y .

Pre-Protocol Analysis will also be performed for the set of all subjects who were randomized to procedure group and completed the study according to the full protocol.

Primary analysis of efficacy will be according to intent to treat (ITT) analysis through the application of:

- 1) **Fisher's exact test** to compare the proportion of success between the test and the control groups, considering that randomization has been diligently conducted and important covariates between the two groups are well balanced.

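### Fisher's exact test is valid but conservative for the primary responder comparison; an exact unconditional test with a pre-specified ordering still holds 5% and raises the chance of significance at no extra subjects

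*Combined protocol and SAP*

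**What the plan says.** Item 1 under Primary Efficacy Outcome Statistical Evaluation Methods applies Fisher's exact test "to compare the proportion of success between the test and the control groups". Rationale for Sample Size agrees with this, planning on "using the Fischer's Exact test to assess the primary endpoint". The design parameters there are "Intended application of a two-tailed test with an alpha value of 0.05 and Power of 0.8", with responder rates of "about 50% of subjects in the test device group and about 20% of subjects in the placebo group".

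The target is "the sample size of 25 available subjects per group" after losses, from "a minimum starting sample size of 30 evaluable subjects in each group". Allocation is equal ("30 subjects in the active procedure group" and the same number in control). The site tables in the sample stratification plan also sum to equal arms: test 7+5+4+3+4+2 = 25, placebo 8+4+4+3+4+2 = 25.

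Two statements bear on what counts as success. The section Primary Efficacy Outcome Measure opens: "Primary efficacy outcome measure for this clinical study will be a statistically significant difference in the proportion of subjects between test and control groups". Under Overall Study Success Criteria, the same section defines success as a difference of at least 30 percentage points between the responder proportions. The plan does not say whether that figure is a second hurdle or a restatement of the design assumption. It does not discuss Fisher's conservatism or any alternative test.

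**The concern.** Randomisation fixes the two arm sizes but not the total number of responders. Fisher's test conditions on that total as well. At this size the conditional distribution takes so few values that much of the nominal 5% cannot be spent. An exact unconditional test fixes only the arm sizes, so it spends more of the 5% while still guaranteeing it.

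What is at stake is the chance of a significant primary result when the device works as assumed. For example, 12/25 v 5/25 (48% v 20%) gives p = 0.072 by Fisher and p = 0.040 by Boschloo. At 30 per arm, 14 v 6 gives 0.054 and 0.030.

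**Working it through.** **Inputs.** Responder rates 0.50 and 0.20, two-sided alpha 0.05, power 0.80, 25 completers and 30 enrolled per arm, all from Rationale for Sample Size. The analysis set (randomised, valid baseline, at least one procedure) puts the analysed number at roughly 25 to 30 per arm.

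**The plan's own figure first.** The usual formula is n = [z(0.975)·√(2·p̄·q̄) + z(0.80)·√(p1·q1 + p2·q2)]² / (p1 − p2)². With p̄ = 0.35 it gives [1.960·√0.455 + 0.842·√0.41]² / 0.09 = 38.5, so 39 per arm (45 with continuity correction). One-sided it gives 31. The unpooled and arcsine variants give 36 and 38 two-sided, 29 and 30 one-sided. None gives 25. The enrolled 30 equals 25 × 1.2; 25/(1 − 0.2) would be 32.

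**Definitions for the test comparison.** All 2×2 tables (a responders of n1, b of n2) were enumerated.
- Fisher p: the sum of hypergeometric probabilities, given a + b, that do not exceed that of the observed table. Reject if p ≤ 0.05.
- Boschloo p: the maximum over a common rate π of the probability of all tables whose two-sided Fisher p is no larger than the observed one. Reject if this is ≤ 0.05.
- Size at π: Σ Bin(a; n1, π)·Bin(b; n2, π) over the rejection region, maximised over a fine grid of π.
- Power: Σ Bin(a; n1, 0.5)·Bin(b; n2, 0.2) over the rejection region.

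With this ordering Boschloo cannot reject less often than Fisher. Given any total, the probability that Fisher's p is ≤ c is at most c. Averaging over totals keeps it at most c, so the Boschloo p never exceeds the Fisher p.

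**Equal arms.**

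| Per arm | Fisher max size | Boschloo max size | Fisher power | Boschloo power | Gain (points) |
|---|---|---|---|---|---|
| 24 | 2.9% | 4.9% | 49.3% | 59.2% | 9.9 |
| 25 | 3.3% | 4.6% | 51.0% | 60.6% | 9.6 |
| 28 | 2.8% | 4.6% | 57.5% | 64.9% | 7.4 |
| 29 | 2.5% | 4.8% | 57.2% | 67.1% | 9.9 |
| 30 | 2.7% | 4.7% | 59.6% | 67.1% | 7.4 |

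At 26 and 27 per arm the gain also lies between 7.4 and 9.9 points.

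**Unequal arms (test/placebo).**

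| Split | Fisher max size | Fisher power | Boschloo power | Gain (points) |
|---|---|---|---|---|
| 25/24 | 4.4% | 53.6% | 57.7% | 4.1 |
| 24/25 | 4.4% | 57.2% | 60.4% | 3.2 |
| 25/27 | 3.9% | 58.4% | 60.3% | 1.9 |
| 28/26 | 3.6% | 60.0% | 65.9% | 5.9 |
| 30/28 | 3.7% | 64.5% | 69.2% | 4.7 |
| 30/25 | 3.7% | 60.8% | 65.9% | 5.0 |

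Twelve such splits were checked. Eleven gave 1.9 to 5.0 points; 28/26 gave 5.9.

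**If the 30-point difference is binding.** At 24, 25 and 30 per arm, every table with an observed difference of at least 30 points already has Fisher p ≤ 0.05. The chance of meeting both conditions at 50% v 20% is 46.7%, 50.5% and 56.1% with either test. At nearby sizes the effect is small. At 26/26, three tables meet the 30-point rule but miss Fisher significance. At 27/25 one does, and the joint chance moves only from 50.35% to 50.45%.

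**The case against.** The strongest objection is that under the stated success rule the change does nothing at the planned sizes. The 30-point difference stands under the heading for overall success, and the alternative hypothesis repeats it. This stands in full if the rule is binding. It does not dispose of the point, because the same section defines the primary outcome by statistical significance, and on that criterion the test matters.

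Four stronger readings are tempting, and the documents or the arithmetic do not support them.
- *That 12/25 v 5/25 would fail only because of the test.* This is true of significance. But the difference is 48 − 20 = 28 points, so the result misses a binding 30-point rule under any test.
- *That the gain is 7 to 10 points in general.* That needs exactly equal arms. Subjects are randomised before the stabilisation week and before the check that the three-day average VAS is at least 50, so some imbalance in the analysed set is likely.
- *That any Boschloo test is at least as powerful as Fisher's.* This fails where the two-sided p-value is a doubled one-sided one, as in scipy's boschloo_exact. For 26/26 v 20/24, Fisher gives 0.046 and the doubled version 0.057. Such tables lie far from 50% v 20%, but they show that the construction must be specified.
- *That the plan contains an error.* Fisher's test is valid, is named consistently in both places, and its conservatism is defensible in a marketing submission.

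It is also fair to say that the sample size is the larger problem and that this change does not cure it.

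**Conclusion.** The point holds as one of efficiency. Fisher's test controls the error rate but spends at most about 2.5% to 3.3% of the 5% with equal arms of 24 to 30, and 3.6% to 4.4% in the slightly unequal splits checked. Ordering by Fisher's two-sided p-value in an exact unconditional test keeps the 5% guarantee. At 50% v 20% it adds about 7 to 10 points of power with equal arms and about 2 to 6 otherwise.

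This rests on the significance criterion deciding the primary outcome, on the plan's assumed responder rates, and on an unstratified comparison without missing data. It gives no benefit at 24, 25 or 30 per arm if the observed 30-point difference is binding. Power stays at about 61% to 67% for 25 to 30 per arm, against the stated 80%.

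**What to change.** In Rationale for Sample Size and in item 1 of the primary evaluation methods, replace Fisher's exact test with an exact unconditional test at two-sided 5%. State that the ordering statistic is the two-sided Fisher p-value, not a doubled one-sided p-value, and fix the software function and version before unblinding. Report the risk difference with an exact unconditional 95% confidence interval, and keep Fisher's p-value as supportive.

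In the same edit, say whether the 30-point difference is a required observed result or only the design assumption, since that decides whether the choice of test affects the success verdict.

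The cost is wording, with no added subjects or visits. The small downside is a less familiar test whose two-sided construction has to be spelled out. The sample size needs its own correction.
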